9. SAFETY REPORTING

9.1 Section 10 WMO event

In accordance to section 10, subsection 1, of the WMO, the investigator will inform the patients and the reviewing accredited METC if anything occurs, on the basis of which it appears that the disadvantages of participation may be significantly greater than was foreseen in the research proposal. The study inclusion will be suspended pending further review by the METC, except insofar as suspension would jeopardise the patients' health. The investigator will take care that all patients are kept informed.

9.2 Definitions in safety reporting

According to EU Directive 90/385/EEC, 93/42/EEC (last amended Directive 2007/47/EC), and 'Guidelines on medical device: MEDDEV 2.7/3', the following definitions are used in the safety reporting:

9.2.1 Investigational medical device

Medical device (Ho-166 poly lactic microspheres) being assessed for safety or performance in this clinical investigation (HEPAR-II)

9.2.2 Device Deficiency (DD)

Inadequacy of the medical device related to its identity, quality, durability, reliability, safety or performance, such as malfunction, misuse or use error and inadequate labelling.

9.2.3 Adverse events (AEs)

Adverse events are defined as any untoward medical occurrence, unintended disease or injury or any untoward clinical signs (including an abnormal laboratory finding) in subjects, users or other persons whether or not related to the investigational device (Ho-166 poly lactic acid microspheres). This also includes events related to the procedures involved (any procedure specified in the clinical investigation plan).

9.2.1 Adverse Device Effects (ADEs)

If an Adverse Event is considered to be related to the use of the investigational medical device then it will be designated an Adverse Device Effect (ADE). This includes any adverse event resulting from insufficiencies or inadequacies in the instruction(s) for use, the deployment, the implantation, the installation, the operation, or any malfunction of the investigational medical device. This also includes any event that is a result of a use error or intentional misuse.

9.2.2 Serious adverse events

A serious adverse event is an Adverse Event that:

- led to a death;
- led to a serious deterioration in health that either:
- resulted in life-threatening illness or injury or
- resulted in a permanent impairment of a body structure or a body function, or
- required in-patient hospitalization or prolongation of existing hospitalization or

- resulted in medical or surgical intervention to prevent life threatening illness or injury or permanent impairment to a body structure or body function
- led to fetal distress, fetal death or a congenital abnormality or birth defect.

This includes Device Deficiencies that might have led to a Serious Adverse Event if a suitable action had not been taken or the intervention had not been made or if circumstances had been less fortunate.

Death of one of the patients who is no longer included in the study will only be reported as a SAE if death occurs within 30 days of the end of the study participation.

Note: A planned hospitalization for a pre-existing condition, or a procedure required by the Clinical Investigation Plan without a serious deterioration in health is not considered to be a serious adverse event.

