Study endpoints	
Primary endpoint:
 
 • Target lesions tumour response 
Secondary endpoints:
 
 • Overall tumour response • Liver specific progression-free survival post ¹⁶⁶Ho-RE • Non-liver specific progression-free survival • Overall survival • Toxicity • Quality of life • Performance status • ^{99m}Tc-MAA and ¹⁶⁶Ho-PLLA-MS scout and therapy dose SPECT/CTs comparison • ¹⁶⁶Ho-PLLA-MS scout dose and total dose MRI comparison • ¹⁶⁶Ho-PLLA-MS scout dose and total dose PET/CT comparison
Duration of treatment	The study consists of a screening phase of approximately 2 weeks followed by a treatment phase of approximately 2-3 weeks. Patients will be followed until liver specific tumour progression or death has occurred, to a maximum of 12 months.
Methodology	A first cohort of 30 patients will be treated with ¹⁶⁶ Ho-RE. After the first cohort, up to 3 additional cohorts of 6 patients will be treated with ¹⁶⁶ Ho-RE. The total number of patients treated in the HEPAR II trial will therefore be at least 30 and at most 48 patients, depending on the observed number of responses. Early termination at a response interim analysis (after 30, 36 or 42 patients) is determined by pre-defined boundaries on the number of observed responses. The boundary in favour of treatment effect may be crossed before 30 patients are reached, but then the study will continue to at least 30 patients to allow estimation of the key secondary endpoints.
Number of study centers	Single center (UMC Utrecht).
Adverse events	All adverse events will be recorded throughout the study.
Inclusion period	Mar 2012 – Aug 2015
Analysis	
Full analysis will be performed after the last patient's last visit. The primary analysis will be to estimate the target lesions tumour response rate (with 95% confidence interval, adjusted for early stopping if indicated). Secondary analysis will be similar estimations of response rates or estimated survival curves (cumulative incidences). Primary and secondary analyses will be based on the Full Analysis Set; analyses on the Per Protocol Set will also be performed and reported.
 
The study will be monitored with stopping boundaries on the number of observed responses. Early termination may occur as a consequence after 30, 36

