3. STUDY DESIGN

Study type	Interventional
Study design	Interventional, treatment, one group, phase II study with a medical device.
Study start date	Mar 2012
Estimated study completion date	Aug 2015

This phase II study comprises a group of at least 30 and at the most 48 patients suffering from liver metastases of primary cancers of miscellaneous origin. Patients who will be included have hepatic metastases not amenable for surgical resection or further systemic treatment. A liver absorbed dose of 60 Gy will be used in each patient in this study. A radiation dose of 60 Gy equates to 3.8 GBq ^{166}Ho /kg liver tissue.

The primary outcome is target lesions tumour response at three months follow-up. For this study, this is defined as: 1) complete response on CT at 3 months, or 2) partial response on CT at 3 months or 3) stable disease on Computed Tomography (CT) at 3 months (see chapter 8.3.1 Definition of treatment success).

This single arm open label study will have a sequential design as follows. Patients will be followed for target lesions tumour response up to 12 months or less if liver specific tumour progression or death occurs. Interim analyses for tumour response achieved are based on sequential decision boundaries. Stopping boundaries are determined such that an overall one-side alpha of at the most 0.05 is maintained in case the true tumour response is 20% ($p_0 \equiv 20\%$). Early termination at a response interim analysis (after 30, 36 or 42 patients) is determined by pre-defined boundaries on the number of observed responses. The boundary in favour of treatment effect may be reached or crossed before 30 patients are reached, but then the study will continue to at least 30 patients to allow estimation of the key secondary efficacy endpoints. Early stopping for proven efficacy can only occur after the first 30 patients are evaluated. Boundaries for early stopping due to futility, i.e. absence of a relevant effect on tumour response, are also included, and are in effect even before the number of 30 patients is reached. The sequential design with boundaries as given in Table 1 will have a power of 90% to reach a positive tumour response decision in case the true target lesions tumour response is 40% ($p_1 \equiv 40\%$). The exact overall one sided type I error is 4.5% [28].

Table 1 Stopping boundaries for early termination at interim analysis.[28] Stopping is indicated if the observed number of responses is at the boundary or beyond.

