8.2 Withdrawal of individual patients

Patients can abandon the study at any time for any reason if they wish to do so without any consequences for treatment or care. The investigator can decide to withdraw a patient from the study for urgent medical reasons.

Patients will be withdrawn from the study if:

- The investigator considers it in the best interest of the patient that he/she be withdrawn
- The patient withdraws consent
- The patient is unable to comply with protocol procedures

The date and reason for withdrawal must be recorded. If the patient withdraws consent after the therapy dose of ^{166}Ho -PLLA-MS has been administered, the patient will be advised to agree to follow-up safety investigations.

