8.2.1 Replacement of withdrawn patients

All patients registered in the study will be accounted for. Patients who do not receive the therapy dose of ^{166}Ho -PLLA-MS will be replaced by another patient, and will not be included in any of the analyses. Based on the (sequential) design and criteria, recruitment and treatment will continue for the first cohort until 30 patients can be evaluated for tumour response. All patients that received ^{166}Ho -RE will be analysed for safety and secondary endpoints, regardless of their availability for tumour response evaluation. For example, a patient that drops out of the study 2 months post treatment will be evaluated for safety and secondary endpoints. However, this patient does not count as one of the 30 patients in whom tumour response needs to be evaluated in the first cohort. Therefore, the patient needs to be replaced. Consequently, if the study continues beyond 30 patients, recruitment will continue in cohorts of 6 patients that can be evaluated for tumour response.

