9.4 Documentation

Attention is to be paid to the occurrence of AEs at all stages of the examination. Thus, the patient should be closely observed by the investigator both during and after the treatment. The recording phase for AEs will start with the first study drug administration and will end the last day of the follow-up period. AEs related to hematological or renal toxicity which are still present at the end of the follow-up period will be followed up until complete resolution as assessed by the investigator. Any adverse events have to be documented in detail as indicated on the E-CRF. The following information is required:

- The date and **time of onset** of any AEs
- The **duration** (the entire duration of an event or symptom, calculated from date of onset and date of end)
- The maximum **intensity** (mild, moderate or severe; for definitions, see below).
- The **drug relationship** of the AE to the investigational product (for definitions, see below)
- Any **study drug action taken** and any other **action taken** by the investigator to resolve the adverse events (entered in free text)
- The **outcome** of the adverse event (recovered completely, recovered with residual effects, continuing).
- An assessment of the **seriousness** of the event will be made by the investigator.

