9.5 Follow-up of adverse events

All adverse events will be followed until they have abated, or until a stable situation has been reached, or until completion of study follow up period. Depending on the event, follow up may require additional tests or medical procedures as indicated, and/or referral to the general physician or a medical specialist.

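### Adverse event collection ends with follow-up, which ends at liver progression, so the safety window is set by efficacy failure or withdrawal and not by the therapy dose

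*Protocol*

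**What the plan says.** **End of follow-up.** The Summary (Duration of treatment) states: "Patients will be followed until liver specific tumour progression or death has occurred, to a maximum of 12 months". Section 3 repeats the limit for tumour response: "up to 12 months or less if liver specific tumour progression or death occurs". Section 11.3.1 likewise makes the number of visits depend on the time to tumour progression.

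**End of adverse event recording.** Section 9.4: "The recording phase for AEs will start with the first study drug administration and will end the last day of the follow-up period". Section 9.5 follows events until they abate, or "until a stable situation has been reached, or until completion of study follow up period". Section 9.4 makes one exception: haematological or renal events still present at the end of follow-up are followed to resolution.

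**Deaths after exit.** Under Section 9.2.2 (Serious adverse events), the death of a patient who has left the study "will only be reported as a SAE if death occurs within 30 days of the end of the study participation".

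**Withdrawal.** Section 8.2 withdraws patients for several reasons, one of them being "The patient is unable to comply with protocol procedures". Only patients who withdraw consent after the therapy dose are advised to accept further safety investigations.

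**Denominator.** Under Section 8.2.1, all patients who received the treatment "will be analysed for safety and secondary endpoints, regardless of their availability for tumour response evaluation". Section 10 defines the Full Analysis Set as all who received the therapy dose. Section 10.2 reports counts and percentages.

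**The concern.** Read together, these rules start the safety clock at the dose but stop it at an efficacy failure or a withdrawal. The patients who fail first are observed for the shortest time, yet each counts as one full patient in every toxicity percentage.

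This matters more here than in most single-arm oncology trials, because the organ treated is the organ whose progression ends observation. Section 8.4 itself says that treatment-related events are hard to tell from those of the underlying disease. If collection stops at liver progression, hepatic events that follow are neither recorded nor attributed.

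The one exception for ongoing events covers blood and kidney. The IDMC's leading toxicity signal in Section 8.4 is hepatic function. Reports to the ethics committee, the IDMC and the competent authority are triggered by serious events (Sections 9.3.4 and 9.3.5), so a death outside the 30 days does not reach them by that route. Section 12.8 intends the data to support a CE-marking application.

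**Working it through.** The protocol states no figure for this point, so there is none to reproduce. The check sets the window rules side by side and then shows what unequal windows do to a crude percentage.

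**Step 1: windows implied by the text.** Inputs: first scheduled response CT at 3 months, maximum follow-up 12 months, 30-day rule for deaths.

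| Patient | AE recording ends | Death counts as SAE until |
|---|---|---|
| Liver progression at the 3-month CT | about month 3 | 3 months + 30 days, about month 4 |
| No liver progression | month 12 | 12 months + 30 days, about month 13 |

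Ratio of AE windows: 12 / 3 = 4.

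Section 8.1.2 also allows a CT at the physician's discretion when progression is suspected, so exit can come earlier. As a constructed case, take exit at week 6 (day 42). AE recording ends there, and a death counts as an SAE up to day 42 + 30 = 72. A death at week 11 (day 77) is 77 − 42 = 35 days after exit and is not an SAE. The week-3 and week-6 laboratory results of that patient do count. The week-9 and 3-month results are no longer due.

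**Step 2: how many patients could have the short window.** Section 3 designs for success rates of 20% and 40% at 3 months. If those rates applied, and every failure ended follow-up at that point:

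- with 48 patients, 48 × 0.20 = 9.6 to 48 × 0.40 = 19.2 would still be followed;
- with 30 patients, 30 × 0.20 = 6 to 30 × 0.40 = 12.

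These are design hypotheses and not forecasts. Failures include deaths, for whom observation ends in any case.

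**Step 3: direction of the bias (illustration, all rates assumed).** Let a share *f* of patients leave at 3 months and the rest be observed for 12. Assume a constant event hazard, the same in everyone, and a risk R over 12 months of complete observation. Then

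- 3-month risk = 1 − (1 − R)^(3/12);
- crude percentage = (1 − f) × R + f × 3-month risk;
- mean months observed = 12(1 − f) + 3f.

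For R = 50%, the 3-month risk is 1 − 0.5^0.25 = 15.9%. For R = 30%, it is 1 − 0.7^0.25 = 8.5%.

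| f | Crude % if R = 50% | Crude % if R = 30% | Mean months observed |
|---|---|---|---|
| 20% | 43 | 26 | 10.2 |
| 40% | 36 | 21 | 8.4 |
| 60% | 30 | 17 | 6.6 |
| 80% | 23 | 13 | 4.8 |

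The crude figure is below the complete-observation figure in every row, and the gap grows with the share leaving early. Toxicity that arises mainly in the first weeks would show much less of this, so the table gives a direction and not an estimate.

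**The case against.** The protocol contains real safeguards:

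- The first scheduled response CT is at 3 months. Most patients who progress therefore keep AE monitoring and laboratory tests at weeks 3, 6 and 9 and at 3 months (Table 2). Where Section 7 gives timing for expected effects, it is mostly days to weeks.
- Dates of death are documented and survival is checked after follow-up through the hospital registration and/or the general physician (Section 8.1.2).
- The IDMC specifically considers patients who discontinued before the 3-month assessment (Section 8.4).
- Section 9.1 obliges the investigator to report unforeseen disadvantages, with no participation window.
- Ongoing haematological and renal events are followed to resolution.

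A longer window would also pick up events caused by progression.

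Most of this stands, and it limits the point to later toxicity, early exits and attribution. It does not remove it. Survival data carry no SAE attribution or prompt reporting, and the IDMC cannot weigh events that were never recorded. Exposure-adjusted rates in a statistical analysis plan could not recover them either.

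A reader might infer more than the documents support:

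- *The IDMC's 30% bilirubin and/or factor V guideline would be missed.* The protocol gives no rates from which to show this. The result appears only if the assumed toxicity rate is set close to the threshold, and the guideline is guidance that the IDMC weighs with other data.
- *Early leavers are counted as event-free.* They are not: anything recorded before exit counts.
- *Deaths after exit are lost.* They lose SAE status and reporting, but not their place in the survival analysis.
- *Withdrawal for inability to comply selects deteriorating patients.* The documents do not say who these patients are. Withdrawal is the weaker limb of the point.

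**Conclusion.** The point holds as a flaw in the collection rules. AE recording runs for about 3 months in a patient who progresses at the first scheduled CT, less after a discretionary CT, and 12 months in a non-progressor: a fourfold difference within one denominator. New non-fatal serious events and new hepatic events after exit have no collection rule, and a death more than 30 days after exit is not an SAE. Later toxicity and its attribution are therefore under-recorded in the patients who fail first, and crude percentages lean low.

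This conclusion rests on the text alone, read so that the end of follow-up at liver progression is also the end of study participation. The size of the bias cannot be computed from the protocol. The percentages in the working rest on an assumed constant hazard and on assumed shares leaving at 3 months. Acute toxicity up to 3 months is mostly captured. The change is worth making because it is cheap, not because a wrong safety conclusion has been shown.

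**What to change.** - **Sections 9.4 and 9.5:** for every treated patient who has not refused, define a minimum safety window from the therapy dose through the 3-month visit. AE recording and the laboratory tests already scheduled in that period continue regardless of liver progression or withdrawal from efficacy follow-up. If the patient cannot attend, obtain the data from the treating physician, which the consent in Section 11.2.1 already covers.
- **Section 9.2.2 (Serious adverse events):** report all SAEs, fatal or not, up to the later of 3 months after the therapy dose or 30 days after exit.
- **Section 8.2:** extend the advice on safety follow-up to every reason for withdrawal.
- **Section 10.2:** because observation still differs after 3 months, also report toxicity percentages for the common 0–3 month window.

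This changes data collection and reporting only. It does not equalise observation after 3 months; the common-window percentages are there to give a figure that does not depend on it. The cost is protocol wording, a few more patient or physician contacts and a few more SAE reports. Toxicity figures may be slightly less favourable and will include some events due to progression.

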9.2.3 Serious Adverse Device Effect (SADE)

Adverse device effect that has resulted in any of the consequences characteristic of a serious adverse event.

9.2.4 Suspected unexpected serious adverse reactions (SUSAR)

Adverse reactions are all untoward and unintended responses to an investigational product related to any dose administered. Unexpected adverse reactions are adverse reactions, of which the nature, or severity, is not consistent with the applicable product information.

9.2.5 Unanticipated Serious Adverse Device Effect (USADE)

Serious adverse device effect which by its nature, incidence, severity or outcome has not been identified in the current version of the safety profile.

9.3 Safety reporting

9.3.1 Recording

All Adverse (Device) Events reported spontaneously by the patient or observed by the investigator or his staff will be recorded.

9.3.2 Report by the investigator to the sponsor

The investigator will report any reportable event to the sponsor within 3 calendar days after the awareness of the occurrence of the event.

9.3.3 Responsible for reporting SA(D)E

In the HEPAR II study the sponsor (Dr [name]) and/or the authorized persons, principal investigator (Dr [name]) and the study coordinator ([name]) will be responsible for reporting.

9.3.4 Reportable events

The following events are considered to be reportable events: any SA(D)E (including SUSAR and/or USADE), any new findings/updates in relation to already reported events

9.3.5 Timelines of reporting

If a SA(D)E indicates an imminent risk of death, serious injury, or serious illness and requires prompt remedial action for other patients/subject, users or other persons or a new finding to it, it will be reported immediately but no later than 2 calendar days after awareness by the sponsor of a new reportable event or of new information in relation with an already reported event. The event will be reported to the accredited METC that approved the protocol. At the same time SA(D)E's will be reported to the members of the IDMC and the national competent authority (IGZ).

All other SA(D)Es will be reported within 7 calendar days after the sponsor has first knowledge of the SA(D)E. At the same time these other SA(D)Es will be reported to the members of the IDMC. The NCA (IGZ) will be reported of other SA(D)E's once every quarter year.

The remaining SUSARs and USADES are also recorded in an overview list (line-listing) that will be submitted once every half year to the METC. This line-listing provides an overview of all SUSARs and USADES from the study device, accompanied by a brief report highlighting the main points of concern.

9.3.6 Reporting standards

The METC will be notified through the web portal ToetsingOnline. The IDMC will receive a copy of this correspondence. The NCA will receive an updated version of the reporting form as required in MEDDEV 2.7/3.

